In this research project we will perform carotid MRI studies in 180 CAD patients with a family history of cardiovascular disease and ApoB ≥ 120 mg/dl (LDL-C levels 100-190 mg/dl). Fifty percent of these subjects will be women. The qualified subjects will be randomized to one of three treatment groups: (1) single therapy - atorvastatin alone; (2) double therapy – atorvastatin plus Niacin (2 g/day); (3) triple therapy – atorvastatin, Niacin plus ezetimibe (10 mg/day). . The treatment target for LDL-C will be ≤ 80 mg/dl for the single and double therapy groups and ≤ 60 mg/dl for the triple therapy group. The HDL-C target for two niacin-treated groups will be 10-12 mg/dl increase. All patients will undergo MRI examination of both carotid arteries annually for three years, a total of 4 examinations. If subjects are enrolled in the trial extension a “late time” scan may be performed at a median time of six years.

Following figure illustrates the study design.

*If subjects are enrolled in the trial extension a “late time” scan may be performed at a median time of six years.

In order to determine if carotid plaque characteristics predict future major cardiovascular events, we will ask the study participants who have completed the original 3-year protocol and carotid MRI examinations to continue on their randomized therapy for up to 11 more years. We will (a) continue to conduct clinical follow-up during the extension to collect cardiovascular events including fatal/non-fatal MI or stroke, hospitalization/revascularization for worsening ischemia, and mortality; (b) determine whether plaque characteristics (lipid content, volume and enhancement) at baseline and its change during therapy are statistically associated with cardiovascular events.

Duration: a mean of 5 years and maximum of 11 years

A.3. Primary Efficacy Parameters:

Primary endpoint: The primary endpoint of this study is carotid plaque lipid composition identified by MRI. The determination of plaque lipid content for each carotid artery will be performed using the automated interactive system. These measurements will be performed from the MRI scans at four time points blinded to time sequence of MRI examinations, patient treatment, lipid levels and clinical course.

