Take One ezetimibe pill and 1-2 pills of Slo-niacin (or half of the daily dose indicated on the bottle) as instructed, with breakfast.

Evening/Night Dosing Directions (PM):

Take 1-2 Atorvastatin pills with dinner, as indicated on the bottle. Take 1-2 pills of Slo-niacin (or half of the daily dose indicated on the bottle) with dinner or before bed.

Valuable Information:

Niacin can sometimes cause a flushing feeling when you first start taking it. If this occurs, there are a few suggestions to help stop or reduce this feeling. The flushing feeling usually goes away over time if you continue to take niacin.

Some helpful ideas for reducing niacin-related flushing:

1. Take your medication in the morning and right before bed.
2. If you use a daily aspirin, take it 30 minutes before your niacin (either morning or evening). Do not take more than 325 mg Aspirin daily without first talking to your doctor.
3. 'Flushing' is reduced by food in your stomach. Enjoy a low-fat snack before you take niacin. An ounce of cheese with a few crackers, a cup of milk or yogurt with fresh fruit are a few examples.
4. Avoid hot drinks, alcohol and spicy foods with dinner as this can sometimes encourage flushing from niacin.

The study medication dispensing process is described under B.11.

B.9. Clinical and Laboratory Follow-up Procedures:

After randomization, the study subjects will be seen monthly for six months and bi-monthly for the remaining 30 months of the 36-month protocol. A total of 22 visits will be conducted for this study as shown in the procedure table below. This clinic visit protocol is developed based on the successful FATS and HATS (RO1 HL49546) clinic visit models. The clinical visits will be done by a team of investigators, coordinators and nurses as well at each of 3 study sites.

Participants who complete the first 3 years of the study and are willing to continue on the randomized therapy and will be followed every 4 months for up to 11 more years.

Table. Clinical Follow-up Protocol

Visit	Entry Criteria	Con-sent	Med. Hx	Family Hx	Vital Signs	Diet Counseling	AE/ Side Effects	Drug Disp.	Com-pliance	Safety Moni-toring	Meds Adj.
Screening	X	X			X						
Baseline		X	X	X	X	X		X			
Non-blood draw visits*					X	X	X	X	X	X	X
Blood draw visits**					X	X	X		X	X	

*: C1, 2, 4, 6, 10, 14, then every 4 months up to C130. **: C3, 5, 8, 12, then every 4 months up to C132.

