At these visits, subjects will undergo questioning about side effects and symptomatic state, and vital signs will be taken. At approximately 60% of the visits, blood will be drawn (<50 ml). The Table below provides the laboratory parameters collected/measured in this study.

Table. Laboratory Measurement Schedule for the Carotid Plaque Composition Study

Visit	S C R.	C o	C 3/ 5/ 8	C 12	C 16/ 20	C 24	C 28/ 32	C 36	Non-annual Visits C40/44/52/56/64 /68/76/80/88/92 /100/104/112/116 /124/128	Annual Visits C48/60/ 72/84/96/ 108/120/132	T X
TC/TG/LDL/ HDL/VLDL	X	X	X	X	X	X	X	X	X	X	X
HDL2&3/IDL/ LDLT/HDLT		X		X		X		X		X	
ApoB, A1, A2, ApoE, Lp(a)	X	X		X		X		X		X	
AST/ALT, CPK		X	X	X	X	X	X	X	X	X	X
BILI/ ALK PHOS/T4/TSH		X									
Creatinine/ Uric Acid		X		X		X		X		X	

Fasting glucose/ HbA1C**	X	X	X	X	X	X	X	X	X	X	X
Insulin/ Fibrino./ HsCRP		X		X		X		X		X	
Plasma storage		X		X				X		X	

*: SCR=screening; Co = baseline; C3, 10, 24, 36,..... = 3, 10, 24, 36,..... months in the study. TX = test for possible side effects of the study treatment. **: This schedule is for diabetic subjects. For non-diabetic patients fasting glucose is measured at S, Co, C12, C24, C36, C48, C60, and every 12 months up to C132.

Dietary counseling will be targeted at weight reduction with goals based on the level of obesity, with additional emphasis on the use of mono-unsaturated fats in a fat-limited (25-30%) diet. Dietary counseling will be provided to subjects by a certified research dietitian.

One week in advance of the next scheduled visits, subjects will receive a form letter from the study coordinators reminding them of the date and time, whether to fast, and to return unused drug supplies. One or two days before the visit they will again be reminded by telephone call from research assistance or the study coordinators, and the visit confirmed or changed. All scheduling is initiated by a computer program with capability to shift dates, making the associated adjustments in compliance calculations and drug distribution. Each clinical visit will take about 30 minutes.

B.10. Study Medication Dispensing

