- (1) Compare current results to baseline or previous values. This helps the investigators determine whether or not study medications could be the possible cause of the abnormal lab value.
- (2) Be thorough in evaluation of patient's side effects and confirm no other changes in life style or other medications could be the cause of such lab value change.
- (3) Determine if the result is only slightly elevated (less than 1.5 x Upper Limit of Normal (ULN) or glucose < 160 mg/dl), monitor patient closely and repeat the test at the next visit usually within 2-4 months per protocol.
- (4) If the result is 1.5-2.5 x ULN ALT/AST or CPK (or glucose ≥ 160 mg/dl), a repeat blood draw will be ordered within 1 month and subject will be closely monitored by telephone follow-up. Subject's primary care physician will be notified and patient will continue the study medications.

(5) If the result is $\geq 3 \times$ ULN ALT/AST or CPK, a repeat blood draw will be ordered within 2 weeks and subject's primary care physician will be notified, the study medications will be reduced or stopped, patient will be monitored closely by telephone follow-up and repeat lab test(s) will be ordered until the values normalize. If glucose >200 mg/dl, home glucose monitoring will be ordered and niacin will be reduced to half dose. If >240 mg/dl, home glucose monitoring will be ordered and niacin will be stopped until glucose levels return to <160 mg/dl.

Steps 3-5 are also outlined in the Table below for Lab Safety Monitoring.

Lab Safety Monitoring Protocol in CPC

	Sample at 3 months		Sample at 5 months		Sample at 8 months and all blood draw visits thereafter	
	Condition	Strategy	Condition	Strategy	Condition	Strategy
AST ALT CPK Safety:	If $<1.5X$ ULN	Careful Monitoring & repeat test @ C5	If $<1.5X$ ULN	Careful Monitoring & repeat test @ C8	If $<1.5X$ ULN	Careful Monitoring & repeat test @ C12
	If 1.5-2.5X ULN	Monitoring. Letter to PCP & repeat test within 1 M	If 1.5-2.5X ULN	Monitoring. Letter to PCP & repeat test within 1 M	If 1.5-2.5X ULN	Monitoring. Letter to PCP & repeat test within 1 M
	If $>3.0X$ ULN	Monitoring. Letter to PCP & repeat test within 2 Wk. Lower or stop meds	If $>3.0X$ ULN	Monitoring. Letter to PCP & repeat test within 2 Wk. Lower or stop meds	If $>3.0X$ ULN	Monitoring. Letter to PCP & repeat test within 2 Wk. Lower or stop meds

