	If ASX and LDLC < 40	Careful monitoring	If ASX and LDLC < 40	Careful monitoring	If ASX and LDLC < 40	Careful monitoring	If ASX and LDLC < 40	Careful monitoring
	If SX and LDLC < 40	Half statin dose or stop meds	If SX and LDLC < 40	Half statin dose or stop meds	If SX and LDLC < 40	Half statin dose or stop meds	If SX and LDLC < 40	Half statin dose or stop meds

SX=symptomatic, ASX=asymptomatic, LCF=low cholesterol flu-like symptoms including muscle aching, nausea and fatigue.

Please note that renal function monitoring is described under Carotid Imaging Protocols below.

D. Carotid Imaging Protocols

[figure not shown]
D.1. MRI Scan Protocol:

Prior to the carotid MRI scans, subjects will be required to fill-out the *Magnetic Resonance (MR) Procedure Screening Form provided by the MRI center (Attachment 1)*. This form will be reviewed by both the study coordinator and by the MRI center staff

to ensure subject's eligibility for MRI scans. For subjects with coronary stents, we will check MRI safety compatibility of a particular stent or surgical implant by visit www.mrisafety.com or contacting the manufacturer directly.

Subjects from the UW and Yakima sites will receive their carotid MRI scans at the Bio-Molecular Imaging Center (BMIC) ([name], Director) for high-resolution animal and human imaging. A 3T Philips Achieva Quasar Dual 3.0T (Software Release 1.2.2) whole body scanner is available for use at this center as a full time research scanner. This scanner also includes the Philips ViewForum Workstation (Software Release 4.1). Subjects enrolled at the USC site will receive their MRI scans at the USC Imaging Center of Department of Radiology using a standard scan protocol designed by the Vascular Imaging Lab at the University of Washington.

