Subjects will be placed in the supine position in the MR scanner with the neck extended to bring the carotid arteries into a more superficial location relative to the skin. A custom designed head holder will be used to minimize patient movement. Two separate phased-array carotid coils will be used for simultaneous bilateral carotid imaging. A standard 3-plane localizer will be used to identify the carotid arteries. Then, 6 more sequences will be applied to generate carotid images. Ten cc of gadolinium contrast material will be administered intravenously through a power injector. Images of 4 locations, centered either on the carotid bifurcation or on the plaque, will be simultaneously acquired using axial 2D spoiled gradient-recalled echo imaging without cardiac gating. These images will be obtained at 10 time points separated by a repetition interval of 15 seconds. Post-contrast T1-weighted images will be acquired 5-7 minutes after gadolinium contrast administration. The total scan time for each patient will be about 50 minutes. Following figure is an example of carotid arteries oblique and cross-sectional views by MRI.

D.2. Renal Function Monitoring:

A gadolinium agent used in this study is FDA-approved. However, in a very small percentage of patients with impaired kidney function, gadolinium has been suspected to cause a side effect called nephrogenic systemic fibrosis, or nephrogenic fibrosing

dermatopathy (NSF/NFD). To monitor the renal function, calculated creatinine clearance will be drawn and glomerular filtration rate (GFR) will be measured within 4 weeks of use of gadolinium agent during the carotid MRI scans. If $GFR < 30 \text{ ml/min/1.73m}^2$ is found at any measurement, or a $\geq 50\%$ drop in GFR from the previous testing point, the subject will be excluded from the study and renal function measurement will be repeated and recorded. If necessary, the subject will be referred to nephrology for further evaluation and treatment.

D.3. MRI Analysis Protocol

1. Image Blinding and Matching Process

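### D.2 excludes a subject from the study after one low or halved GFR; its gadolinium rationale supports withholding contrast, not ending visits, laboratory tests and event collection

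*Combined protocol and SAP*

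**What the plan says.** D.2 (Renal Function Monitoring) requires a GFR within four weeks of each gadolinium scan. It sets two triggers: any value below 30 mL/min/1.73 m², or a fall of at least half since the previous test. On either, "the subject will be excluded from the study and renal function measurement will be repeated and recorded", with nephrology referral if needed. The only reason stated is nephrogenic systemic fibrosis from gadolinium in impaired kidneys. C.3 (Safety Monitoring Procedures) adds no renal rule of its own; it closes by noting that "renal function monitoring is described under Carotid Imaging Protocols below".

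Other sections that bear on the point:

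- B.2, exclusion 7, bars GFR of 59 or less before randomisation.
- A.2 invites into the extension those "who have completed the original 3-year protocol and carotid MRI examinations". B.9 words the same invitation without naming MRI: "Participants who complete the first 3 years of the study and are willing to continue on the randomized therapy".
- The B.9 laboratory table has a row for "Creatinine/ Uric Acid" at baseline and yearly to month 132.
- For ALT/AST or CPK at three times the upper limit or more, C.3 says "the study medications will be reduced or stopped, patient will be monitored closely by telephone follow-up", with repeat tests until values return to normal.
- F.3 item 4, branch (i), splits each person's time at the 3-year MRI: one interval from baseline to an event or that scan, a second from that scan onward, always using the latest MRI data.

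**The concern.** The remedy is wider than the reason for it. A contrast hazard is met by giving no more contrast. Deaths, infarctions, strokes and revascularisations, clinic visits and blood tests need no gadolinium. If exclusion means what it ordinarily means, the trial stops observing a randomised subject because of a health event after randomisation. It also stops the scheduled yearly creatinine in the subjects with the worst renal signal. The repeat test is not made a condition of exclusion, and no way back is described if it is normal.

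The baseline scan of such a subject has already been done and could still inform the event analysis if events went on being collected. Even if D.2 is read narrowly, A.2 leaves it unclear whether someone who missed contrast scans for renal reasons may be followed in the extension.

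**Working it through.** The documents give no figure for this rule, so there is nothing to reproduce. The check has two parts.

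**1. Does the reason reach the remedy?**

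- The percentage trigger can fire well above D.2's own limit: a fall from 110 to 55 is 55/110 = 50%, which excludes a subject whose GFR is 55.
- Entry requires GFR above 59. At entry a subject cannot be near 30, so the rule acts in practice on randomised subjects at the follow-up tests. A one-step fall from 60 to 30 is already a 50% drop.
- The plan's liver and CPK rules reduce or stop drugs and keep the subject monitored, and its glucose rules halve or stop niacin. None of them excludes the subject.
- No section found in these documents keeps an excluded subject in visits, laboratory tests or event collection.

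**2. How much follow-up is at stake?**

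Inputs from the documents:

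- Up to 240 enrolled (A.4).
- Scans at baseline and years 1, 2 and 3 (A.2).
- "Duration: a mean of 5 years and maximum of 11 years" (A.2).
- Subjects "seen monthly for six months and bi-monthly for the remaining 30 months of the 36-month protocol" (B.9), which gives 1 baseline + 6 monthly + 30/2 = 15 bi-monthly = 22 visits, matching the stated total.

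Assumptions, because the documents give no values: 0.5% to 5% of subjects trigger, triggers are spread evenly over the three follow-up tests, and there is no other attrition. The possible late scan in the extension is not counted.

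Subjects affected: 0.005 × 240 = 1.2 and 0.05 × 240 = 12.

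Loss per subject for a trigger at year t:

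| Trigger | To 3-year scan (3 − t) | To 5-year mean (5 − t) | Visits of 22 |
|---|---|---|---|
| Year 1 | 2 years | 4 years | (36 − 12)/2 = 12 |
| Year 2 | 1 year | 3 years | (36 − 24)/2 = 6 |
| Year 3 | 0 years | 2 years | 0 |
| Even split | 1 year | 3 years | 6 |

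Totals under the even split:

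- Branch (i), first interval: 1.2 × 1 = 1.2 and 12 × 1 = 12, of 240 × 3 = 720 person-years (0.2% and 1.7%). Extremes: none if all trigger at year 3; 2.4 to 24 (0.3% to 3.3%) if all trigger at year 1.
- Event records to the 5-year mean: 1.2 × 3 = 3.6 and 12 × 3 = 36, of 240 × 5 = 1,200 person-years (0.3% and 3.0%). Extremes: 1.2 × 2 = 2.4 and 12 × 4 = 48 (0.2% and 4.0%).
- Protocol visits: 1.2 × 6 = 7.2 and 12 × 6 = 72, of 240 × 22 = 5,280 (0.1% and 1.4%).

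The first line is the loss to the planned event analysis. Branch (i) starts its second interval at the 3-year MRI, so a subject without that scan contributes nothing after year 3 as the plan is written. The second line is the larger loss of event and safety records. Those records would enter branch (i) after year 3 only if the plan let the last available scan be carried forward. Branch (ii) needs change up to the 3-year scan, so lipid and enhancement change stays missing there if that contrast scan is not done.

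**The case against.** The strongest reply is that D.2 never says follow-up ends. It sits among the imaging protocols, keeps the subject under repeat renal testing and referral, and gives no order between the exclusion and the repeat test. E.1 also lists extension protocols and a procedure manual that are not part of these documents and might contain a retention rule. This stands as a limit on certainty: the broad reading is the plain one, but it is a reading. It does not remove the need for a fix, since the wording is exclusion from the study and several sites must apply it alike.

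The second reply is that triggers should be rare. Entry excludes GFR of 59 or less, and also poor glucose control and uncontrolled hypertension. That stands, and it keeps the point minor.

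The third is that little of the planned analysis depends on it. That largely stands. The primary endpoint is plaque lipid, and tissue classification uses the post-contrast series, so retention recovers no lipid or enhancement data at a missed contrast scan. Enrolling 240 for 180 completers already allows for 1 − 180/240 = 25% attrition.

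A reader might infer that the rule damages the comparison of arms or costs power. The documents do not support that: the rule is the same in all arms, nothing shows that it triggers differently by arm, and F.3 item 4 plans no comparison of events between arms. A reader might also count all the years to the 5-year mean as lost to branch (i); the way that branch defines its intervals rules this out. Loss prompted by worsening renal function could be informative for the event analysis, but the documents give no data to show that it is.

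**Conclusion.** The point holds as a minor one. D.2 states a rule whose only given reason justifies withholding gadolinium. On its plain reading the rule also ends observation of randomised subjects, and nothing in these documents retains them. On the assumed trigger rates it touches about 1 to 12 subjects and about 0.2% to 1.7% of the person-years in branch (i)'s first interval. A somewhat larger share of event and safety records to the mean duration is also lost. The rates and the even spread over years are assumptions; the per-subject losses follow from the schedule. The clearest harm is to safety observation: the scheduled visits and yearly creatinine stop for the subjects who most need them. That a review of study drugs is reasonable is a clinical judgement; D.2 itself does not mention study drugs.

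**What to change.** Three short changes:

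- **D.2:** replace the exclusion clause with: *the subject receives no further gadolinium unless a repeat test shows recovery and the clinicians agree; study drugs are continued, reduced or stopped at the clinicians' discretion; the subject continues visits, laboratory tests and event follow-up and is analysed in the randomised arm.*
- **A.2:** state that contrast scans missed for renal reasons do not prevent event follow-up in the extension.
- **F.3 item 4, branch (i):** state that a subject with no 3-year scan stays at risk, with the most recent available scan as the covariate.

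The visits and yearly creatinine tests are already scheduled, so no new visit or test type is needed. The cost is a short amendment through each site's IRB (A.5 notes that the two sites outside the University of Washington hold their own approvals) and continued visits for a few subjects. Contrast protection is not weakened: gadolinium stops at the trigger and resumes only after demonstrated recovery and clinical agreement. Carrying the last scan forward after year 3 means using an older plaque measurement for those few subjects, and the report should say so.

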Official Title: Carotid Plaque Composition by Magnetic Resonance Imaging During Lipid Lowering Therapy

NCT00715273

Study Protocol and Statistical Analysis Plan - 06APR2016

This final protocol version reflects the extension of clinical events monitoring and open-label study as supported by American Heart Association and Alpha Phi grants.

Responsible Party:

Principal Investigator

[name] [[name]]

Professor

University of Washington, Seattle, WA, USA

Study Protocol and Procedures (April 2016)

Study Title: CAROTID PLAQUE COMPOSITION BY MRI DURING LIPID-
LOWERING, supported by NHLBI (R01 HLO63895)

Short title: CPC

A. Study Protocol

A.1. Study Objectives/Aims:

(1) To test the primary hypothesis that intensive lipid therapy decreases carotid plaque lipid content assessed by CE-MRI. To achieve this goal, we will (a) perform carotid CE-MRI scans for all 180 study subjects at baseline, 1, 2, and 3 years; (b) perform quantitative assessments of plaque lipid content; (c) compare the plaque lipid content between pre- and post-treatment for all 3 therapy groups; (d) demonstrate the time-course of plaque lipid content change during intensive lipid modification over 3 years by assessing serial carotid CE-MRI examinations.

(2) To test the secondary and exploratory hypotheses that intensive lipid therapy is associated with plaque regression and decreased plaque enhancement assessed by CE-MRI. To achieve this goal, we will (a) perform quantitative assessments of plaque volume and enhancement; (b) compare the plaque volume and enhancement between pre- and post-treatment for all 3 therapy groups; (c) examine the relationship between plaque lipid and volume and enhancement characteristics; (d) demonstrate the time-course of plaque volume and enhancement change during intensive lipid modification over 3 years.

(3) To examine the association of factors including clinical risk factors, lipids, lipoprotein heterogeneity, inflammatory markers, oxidative stress markers and carotid plaque characteristics (lipid, volume, and enhancement). To achieve this goal, we will (a) perform laboratory testing on lipids, lipoprotein heterogeneity, inflammatory markers, oxidative stress markers at baseline and on therapy; (b) describe the change in each of these measurements between baseline and on treatment; (c) determine the statistical significance of each measured risk variable and its change in relation to the change in plaque characteristics.

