(4) To investigate the effects of HDL-raising and very intensive LDL-lowering on carotid plaque characteristics over 3 years. To achieve this goal, we will (a) perform quantitative assessment of plaque lipid, volume, and enhancement at all 4 time points blinded to the MRI time sequence and treatment; (b) compare the change in plaque characteristics over 3 years between single and double therapy for HDL-raising effect, between double and triple therapy for more intensive LDL-lowering effect, and single and triple therapy for more LDL-lowering plus HDL-raising effect.

(5) To determine if carotid plaque characteristics predict future major cardiovascular events. To achieve this goal, we will (a) continue to conduct clinical follow-up for a median of 5 years to collect cardiovascular events including fatal/non-fatal MI or stroke, hospitalization/revascularization for worsening ischemia, and mortality; (b) determine whether plaque characteristics (lipid content, volume and enhancement) at baseline and its change during therapy are statistically associated with cardiovascular events.

[figure not shown]
This study employs the state-of-the-art technique to assess both the magnitude and mechanisms of benefit of lipid therapy. It will be one of the first studies to examine the effects of lipid-lowering therapy on human atherosclerotic plaques in vivo and will provide novel insights into our understanding of atherosclerotic plaque pathology and the mechanisms of lipid-lowering therapy preventing ischemic events.

A.2. Study Design:

This project is a randomized open-label study.

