Step 3. Registration: After manual boundary detection, the CASCADE Program will automatically identify and outline the lumen and wall boundary of the carotid artery in the remaining 4 sequences. An example is shown in Figure 3 below. Expert readers will review the outlines generated by CASCADE, and have the opportunity to manually override errors in the automated outlines that may occur as a result of marginal image quality or flow artifact.

Step 4. Auto-segmentation: The CASCADE Program will automatically identify and quantify the tissue component within the arterial wall. Expert readers will then review the output of CASCADE to insure correct classification of the plaque components. An example is shown in Figure 4 below with loose matrix in purple and lipid content in yellow.

The image analysis for this study will be performed at the time of completing both MRI examinations. By doing so, a region of each carotid artery, covered by both baseline and 2-year scans, will be identified and image analysis will be performed within the region. This will allow the same reviewers to analyze all images and therefore to reduce the inter-reader variability. The analysis will be performed at Vascular Imaging Lab using CASCADE with automated tissue segmentation capability using MEPPS.

(c) Plaque Tissue Composition: This will be calculated based on each identified tissue volume and wall volume at each given location: tissue volume/wall volume x (100%), and presented as percentage.

(d) Summary of Plaque Variables: CASCADE can produce a list of comprehensive plaque assessments. Plaque burden measurements will include the carotid lumen, wall, and outer-wall area in mm², wall thickness in mm, and wall/outer-wall ratio (a normalized wall index that is adjusted for carotid artery size difference) that is equivalent to the % of atheroma area used in the coronary intravascular studies. The plaque tissue characteristics will be presented as absolute measurement in mm² and as a proportion of the corresponding vessel wall area, expressed as in % lipid, % loose matrix, % calcium, % fibrous tissue and % hemorrhage. Additionally, the plaque integrity will also be evaluated and described as ruptured, thin or thick fibrous cap, with and without ulceration, with and without thrombus.

[figure not shown]

Ultrasound Examination:

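### D.3 sets the measured carotid region from the baseline and 2-year scans, but the main change tests use baseline and year 3, so a matched segment is not assured

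*Combined protocol and SAP*

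**What the plan says.** **The reading rule.** D.3 item 3(b), after Step 4, says: "The image analysis for this study will be performed at the time of completing both MRI examinations". It then restricts measurement to a region of each carotid "covered by both baseline and 2-year scans, will be identified and image analysis will be performed within the region", and gives the reason: "This will allow the same reviewers to analyze all images and therefore to reduce the inter-reader variability".

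**The scan schedule.** Aim 1(a) in A.1 is to "perform carotid CE-MRI scans for all 180 study subjects at baseline, 1, 2, and 3 years". A.2 and F.1 also give four examinations. The ultrasound section places its exams on the MR dates, which it lists as baseline and months 12, 24 and 36.

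**The endpoint.** A.3 says of plaque lipid content: "These measurements will be performed from the MRI scans at four time points blinded to time sequence of MRI examinations". Aim 4(a) is to "perform quantitative assessment of plaque lipid, volume, and enhancement at all 4 time points blinded to the MRI time sequence and treatment". D.3 item 1 replaces scan identifiers and dates with random IDs so that readers do not know the time order.

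**The analyses.** F.3 item 2 uses paired t tests of baseline against 3 years. F.3 item 3 compares treatment groups on the change from baseline to the 3-year MRI and uses the same change as the regression outcome. F.3 item 4(ii) uses the rate of change over the first 3 years. Aim 1(d) adds a time course: "demonstrate the time-course of plaque lipid content change during intensive lipid modification over 3 years by assessing serial carotid CE-MRI examinations".

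**The concern.** Percent lipid is the primary endpoint, and it depends on which slices are measured. The authors evidently saw this, since they limit reading to a shared region and have the same reviewers read everything. But the one rule that sets a shared region across visits names the 2-year scan as the follow-up, while the main tests use the 3-year scan. Read literally, its timing phrase also belongs to a two-scan study.

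What is at stake is whether the baseline and 3-year values describe the same stretch of artery and were read in the same way. The most exposed analysis is the pre/post comparison, since aim 1(c) is to "compare the plaque lipid content between pre- and post-treatment for all 3 therapy groups" and a within-group difference has no control to absorb a measurement shift.

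**Working it through.** There is no stated figure to reproduce, so the check sets the sections side by side.

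**Step 1: which scans each section uses.**

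| Source | Baseline | Year 1 | Year 2 | Year 3 |
|---|---|---|---|---|
| Schedule (A.1, A.2, F.1) | yes | yes | yes | yes |
| Endpoint measurement (A.3, aim 4(a)) | yes | yes | yes | yes |
| Region rule (D.3 item 3) | yes | no | yes | no |
| Main change tests (F.3 items 2, 3, 4(ii)) | yes | no | no | yes |

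The region rule names 2 of the 4 scans. It shares only the baseline scan with the main change tests.

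**Step 2: the two ways to read the rule.**

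- *Narrow reading.* The rule governs only the baseline and 2-year scans. The 3-year scan is then measured with no stated region.
- *Broad reading.* The overlap of the baseline and 2-year scans becomes one fixed region, and every image, including year 3, is read within it. A common region then exists. But it was chosen without the 3-year scan, and nothing says what to do if that scan covers only part of it.

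Neither reading assures that the baseline and 3-year values come from the same segment.

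**Step 3: whether other text fills the gap.**

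- D.3 item 1 and Step 1 of item 3(b) use the bifurcation to align contrast weightings with one another. This gives every examination the same anatomical reference and limits gross mismatch. It does not say which slices are compared between years.
- D.3 item 3(c) computes composition location by location, but does not pair locations across visits.
- F.3 item 1 averages per slice. That controls for how many slices there are, not where they lie.

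**Step 4: noise or bias.** Write the observed 3-year change in one subject as D = d + e, where d is the true change and e is the part due to unmatched coverage.

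- Mean of D = mean of d + mean of e.
- If e is independent of d, variance of D = variance of d + variance of e.

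If coverage shifts have no preferred direction, the mean of e is zero and only the variance grows. If the mean of e is not zero, the pre/post test carries it as bias. The between-group contrast carries only the difference in mean e between arms. With readers blinded to treatment, the documents give no reason to expect one.

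**Step 5: timing.** D.3 does not say whether the two examinations are counted per subject or once for the whole study. If reading took place per subject at year 2, the 3-year scan would be read in a later session. Reader drift could then enter e with a consistent sign, and the practice would conflict with the four-time-point blinded reading in A.1, A.3 and D.3 item 1.

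**Step 6: size.** The variance and mean of e would need a slice count for the composition reading, a positioning tolerance or a scan-rescan repeatability. The documents give only the 2 mm slice thickness, so no figure can be derived.

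**The case against.** The strongest reply is that this is leftover wording and the imaging laboratory would match the scans anyway. The two-year change used as an example in F.3 item 5 fits that account. It remains an inference: the document calls itself the final protocol version, and its text names specific scans.

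A second reply is that the broad reading already supplies a common region. That is a fair reading, and it means the documents do not support the claim that no common region exists at all. What survives is narrower: the 3-year scan plays no part in choosing that region.

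A third is that head positioning (D.1) and the bifurcation landmark make gross mismatch unlikely. This stands as a limit on the size of the problem. It does not replace a rule for which slices are compared.

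A reader might also infer that the 3-year scan is not measured, or that blinding to time sequence was abandoned. The documents support neither. A.1 and A.3 require all four time points to be read blinded to time sequence, and only the timing phrase in D.3 is at odds with that. Nor does the gap show that the treatment comparison is biased, because shifts of random sign add variance and the readers are blinded to treatment.

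**Conclusion.** Wrong as written. An operational rule for the primary endpoint names a follow-up scan other than the one used in the main change tests. This holds on either reading of the rule and rests on no assumption.

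The consequence is more modest. The likely effect is extra noise in the baseline-to-3-year change, and so some loss of precision. Bias in the uncontrolled pre/post test is possible only if coverage shifted systematically or the 3-year scans were read in a later session, and the documents establish neither. The size cannot be computed from what they give.

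The cross-sectional event analysis in F.3 item 4(i) uses plaque status rather than within-subject change, so it does not depend on matching baseline to year 3. The two-year example in F.3 item 5 is an editorial matter.

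**What to change.** In D.3 item 3, replace the reference to two examinations and to the baseline and 2-year scans with text that states:

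1. **Reading.** Each subject's protocol scans are read together by the same reviewers, under the random IDs and blinded to time sequence, after the 3-year scan. If that scan is missed, reading follows the last protocol scan obtained.
2. **Main change.** The baseline-to-3-year change is measured in the region covered by both the baseline and the 3-year scan.
3. **Time course.** Either one region common to all available scans or a separate region for each pair may be used, and the plan should say which. Pairwise regions give a different baseline value for each comparison. One common region may be shorter.
4. **Late scan.** The optional scan in the extension neither delays reading nor defines the region.

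If reading has already been done, state the region and the reading order actually used.

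The cost is wording, with no extra scans or readers. Reading waits until year 3, and the matched region may be shorter than the coverage of a single scan.
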